7.2.2. New Subjects

New Subjects will be excluded from participation in this trial if they meet any of the following criteria:

4. Have any current “primary” Axis I diagnosis other than MDD, where “primary” is defined by the investigator as the primary source of current distress and functional impairment
5. Have any of the following psychiatric conditions per DSM-IV-TR criteria, as assessed by the MINI. Conditions not assessable by the MINI should be assessed by clinical judgment:
 - a. Lifetime history of an Axis I diagnosis of dementia, schizophrenia or other psychotic disorder (including psychotic depression), or bipolar disorder (I or II)

- b. History within the past 12 months of an Axis I diagnosis of eating disorder, posttraumatic stress disorder, or acute stress disorder
 - c. Clinically significant current Axis II diagnosis of borderline, antisocial, paranoid, schizoid, schizotypal, or histrionic personality disorder
 - d. Current diagnosis or clinical evidence of any cognitive disorder at screening
6. Have experienced hallucinations, delusions, or any psychotic symptoms in the current MDE
 7. Have initiated psychotherapy within 6 weeks of screening
 8. Have received adjunctive therapy at an adequate dose and duration in combination with their approved ADT for the purpose of augmenting the effects of the ADT at any time during the current MDE (such adjunctive therapies include, but are not restricted to: atypical antipsychotics, monoamine oxidase inhibitors, lithium, tricyclic antidepressants, psychostimulants, bupropion, and BUP)
 9. Have been hospitalized for MDD within 3 months prior to screening
 10. Have used opioid agonists (eg, codeine, oxycodone, tramadol, morphine) or opioid antagonists (eg, naloxone, naltrexone) within 14 days before screening, or have an anticipated need for opioid use at any point during the study (eg, planned surgery)
 11. Have used an extended-release formulation of an opioid antagonist within 2 months prior to screening
 12. Have initiated a hypnotic agent for insomnia (eg, benzodiazepines, zolpidem, trazodone) within 30 days prior to screening. Have used a hypnotic agent for insomnia >3 times/week within 30 days of screening, or expect to use any of these agents at >3 times/week at any time during the study. Have used a hypnotic agent for any indication other than insomnia within 30 days prior to screening (see [Section 8.4.2.2](#) for further details)
 13. Have initiated or had dose adjustment to hormone replacement therapy (including testosterone) or an oral contraceptive within 30 days of screening
 14. Have used inducers or moderate to strong inhibitors of cytochrome P450 (CYP) 3A4 (prescription medications, over-the-counter medications [OTC], or dietary supplements) within 30 days prior to screening (see [Appendix A](#) for examples of prohibited CYP3A4 modulators)
 15. Have received electroconvulsive therapy treatment within the last 2 years, or received more than 1 course of electroconvulsive treatment during their lifetime
 16. Pose a current suicide risk, as evidenced by any of the following:
 - a. it is the opinion of the investigator that the subject may be at risk for suicide
 - b. the subject responds “Yes” to Question # 4 (“Active Suicidal Ideation with Some Intent to Act, Without Specific Plan”) or Question # 5 (“Active Suicidal Ideation with Specific Plan and Intent”) on the Baseline Columbia Suicide Severity Rating Scale (C-SSRS), if the most recent episode occurred within the past 12 months
 - c. the subject has attempted suicide within the past 2 years

17. Have a QT interval >450 msec for men and >470 msec for women, assessed in a relaxed state, as corrected by the Fridericia formula (QTcF) observed at Visit 1 or Visit 2
 18. Have an aspartate aminotransferase or alanine transaminase measurement of >2 times the upper limit of normal at Visit 1.
 19. Have current evidence of or history of any of the following:
 - a. compromised respiratory function (eg, chronic obstructive pulmonary disease, respiratory depression, signs or symptoms of hypoxia at screening)
 - b. thyroid pathology (unless stabilized and euthyroid for >3 months at the time of screening)
 - c. seizure disorder (excluding febrile seizures)
 - d. hepatitis or human immunodeficiency virus (HIV) infection
 - e. myasthenia gravis
 - f. any contraindicated medical condition as per the approved labeling for buprenorphine
 20. Have current evidence of, or a history in the past 12 months of, alcohol or substance abuse or dependence (excluding nicotine) per DSM-IV-TR criteria as assessed by the MINI
 21. Have a positive breath alcohol test at screening
 22. Have a history of intolerance, allergy or hypersensitivity to BUP or opioid antagonists (eg, naltrexone, naloxone)
 23. Have had a significant blood loss (>500 mL) or blood donation (including platelets or plasma) within 60 days of screening or between screening and randomization, or anticipated blood donation at any time during the trial
 24. Have participated in any of the following:
 - a. clinical studies of more than 2 distinct investigational products with a central nervous system indication in the past 4 years
 - b. any clinical study of an investigational product given as an adjunctive treatment for MDD at any time during the current MDE
 - c. any clinical study of an investigational product and/or have received an investigational drug or device within 30 days of screening
 25. Are an employee of the investigator or study center, or immediate family* of such employees or the investigator
 26. Are an employee or an immediate family member* of an employee (permanent, temporary contract worker, or designee responsible for the conduct of the study) of Alkermes or the contract research organization (CRO) executing this study or any prior ALKS 5461 study
- * Immediate family is defined as a spouse, parent, child, or sibling, whether biological or legally adopted

7.3. Subject Withdrawal

Any subject who signs the informed consent form for this study but does not qualify for ALKS 5461 dosing will be considered a screen failure.

A subject may be discontinued from the study at any time if the subject, investigator, or sponsor determines that it is not in the best interest of the subject to continue participation.

Examples of reasons for subject discontinuation may include, but are not limited to, the following:

- Failure to meet eligibility criteria
- Adverse Event
- Lack of Efficacy
- Physician's decision
- Pregnancy (see [Section 8.4.1](#))
- Protocol violation
- Non-compliance with study drug
- Withdrawal of consent
- Lost to follow-up
- Study terminated by Sponsor
- Other

The investigator must maintain a record of all subjects who fail to complete the study. A full explanation of the reason for study discontinuation will be made on the appropriate electronic case report form (eCRF) and/or IxRS. The reason for discontinuation will be documented. If a subject is lost to follow-up, a reasonable attempt to contact the subject must be made and documented.

If a subject withdraws from the study for any reason, any ongoing adverse events (AEs) will be followed until resolution, until deemed stable by the investigator, or until the subject is deemed by the investigator to be lost to follow-up. If, in the opinion of the investigator, it is necessary to monitor a subject beyond the safety follow-up period, the follow-up period may be extended as necessary. In such instances, the sponsor and the investigator will agree to an acceptable follow-up schedule.

In the event that a subject chooses to withdraw from the study, the investigator should make a reasonable effort to ascertain the reason(s) for withdrawal, while fully respecting the subject's rights to do so. Subjects will be asked to return to the clinic for an early termination visit and follow-up visits. The early termination visit should be scheduled within 24 hours of the subject's last dose and will mirror the assessments scheduled to be collected at Visit 14. Following the early termination visit, subjects will be asked to participate in the safety follow-up period as detailed in [Table 3](#). If the subject fails or refuses to return to the study center for clinic visits, an attempt must be made to contact the subject by telephone in order to assess as many safety and

efficacy parameters as possible. All data collected over the telephone must be documented and kept in the subject's record.

7.4. Replacement of Subjects

Subjects who withdraw after receiving the first dose of study drug in this study will not be replaced.

8. STUDY DESIGN

8.1. Overall Study Design and Plan

This is a multicenter, multinational, study to evaluate the long-term safety and tolerability, and to explore treatment effect of 52 weeks of ALKS 5461 administration for use as an adjunctive therapy to antidepressants for the treatment of MDD in subjects who have had 1 to 2 inadequate responses to an approved ADT. All subjects in the study will have been treated with an adequate dose of an approved ADT for at least 8 weeks, at a stable dose over the last 4 weeks prior to study entry. An adequate dose is defined as the minimum effective dose or higher according to the applicable current approved label, inclusive of up to 1 week for titration into the adequate dose range.

Subjects will enter into the study in one of three ways, based on their previous experience with ALKS 5461:

1. New Subjects: those who have not randomized in a prior study of ALKS 5461 within 2 years
2. Continuing Subjects: those who have completed the treatment period of study ALK5461-205, ALK5461-206, ALK5461-207, or ALK5461-210 within the past 10 days
3. Lead-in Subjects: those who participated in study ALK5461-205, ALK5461-206, or ALK5461-207 and have completed the PLI within the past 10 days, and met the criteria for response to ADT during the PLI period of that antecedent study, but did not meet the criteria for remission. Criteria for completion of the PLI includes 1) at least 8 weeks of ADT with at least 5 weeks at the minimally effective dose and 2) completion of Visits 1a through 1f.

All New Subjects will be initially evaluated for eligibility at screening (Visit 1), to occur up to 28 days prior to Visit 2.

For Lead-in and Continuing Subjects, Visit 2 will be the first visit of this study and there will not be a separate screening visit.

While completion of Visit 2 of the antecedent study for Lead-In Subjects is not required, if a subject has completed a Visit 2 of the antecedent study, completed assessments taken at Visit 2 of the antecedent study do not need to be repeated at Visit 2 of this study unless more than 10 days elapses between these visits.

For Continuing Subjects, Visit 2 of this study must occur within 10 days of the subject's end of treatment visit in the prior study. Completed assessments taken at the end of treatment visit of the antecedent study do not need to be repeated at Visit 2 of this study. At Visit 2, all eligible, consenting subjects will begin the treatment period. Subjects entering the study already receiving ALKS 5461 will not require titration; all other subjects will require a 1-week ALKS 5461 titration period. Depending on the antecedent study, the titration may be blinded. Regardless of method of entry, all subjects will have been taking an SSRI, SNRI, or bupropion for at least 8 weeks at the beginning of the treatment period (Visit 2), and at an adequate dose for at least

5 weeks. Table 1 below shows the Week 1 titration and blinding schemes for the subjects entering by each path.

Table 1: Week 1 Titration and Blinding by Entry Dose and Antecedent Study

Dose Upon Study Entry	Antecedent Study	Week 1 Blinding	Week 1 Dosing Scheme
No study drug being given	
 New Subjects Lead-in Subjects ALK5461-205 (after 1-week discontinuation period) 	Unblinded	1-Week Titration 
 Days 1–3: ALKS 5461 0.5/0.5 Days 4–7: ALKS 5461 1/1
Placebo	
 ALK5461-206 ALK5461-207 	Blinded	
 Days 8–364: ALKS 5461 2/2
ALKS 5461 1/1	
 ALK5461-207 	Blinded	No Titration 
 Days 1–364: ALKS 5461 2/2
ALKS 5461 2/2	
 ALK5461-206 ALK5461-207 	Blinded	
	
 ALK5461-210 	Unblinded	

Dosing is described in detail in [Section 9.1.2](#). From Week 2 to 52, all participating subjects will take ALKS 5461 2/2 and an approved ADT, with allowable dose adjustments for tolerability as described in [Section 9.5](#).

Study staff will administer the first dose of ALKS 5461 at Visit 2 (Day 1). From that point on during the treatment period, according to the schedule of visits as shown in [Table 2](#), the staff will dispense ALKS 5461 for subjects’ self-administration. Subjects will be advised to take the study drug at bedtime.

During the 52-week treatment period, subjects will return to the clinic for periodic scheduled visits (Visits 2-14) at which safety, tolerability, and treatment effect over time will be assessed.

A 4-week safety follow-up period will occur following the ALKS 5461 treatment period. During the 4-week follow-up period, there are a total of 4 clinic visits (Visits 15-18), as well as 7 safety assessments by phone. The clinic visits will occur 1 day, 1 week, 2 weeks, and 4 weeks following the end of treatment visit (Visit 14). The phone assessments will occur daily for the first week between visits, and weekly during the second and third week. See [Table 3](#) for the schedule of assessments during the follow-up period.

If any AEs are reported that relate to opioid withdrawal (eg nausea, vomiting, restlessness, hyperhidrosis) during a phone assessment in the follow-up period, the subject will be asked to come into the clinic as soon as possible to receive a Clinical Opiate Withdrawal Scale (COWS) assessment.

After completing the study, ADT may be continued for up to 3 months, as appropriate, based on the investigator’s clinical judgment.

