3.7.3. Adverse Events of Special Interest

Adverse events of special interest (AESIs) will be summarized by Preferred Term and by prior ALKS 5461 exposure and overall during treatment period for the Safety Population / Post-discontinuation Safety Population for any TEAEs or PDEAEs of special interest. The following summaries will be created for AESI:

- TEAEs associated with abuse potential
- TEAEs associated with dependence
- PDEAEs associated with withdrawal
- TEAEs associated with suicidal ideation and behavior
- TEAEs associated with hypomania / mania
- TEAEs associated with central nervous system (CNS) depression and sedation
- TEAEs associated with respiratory depression
- TEAEs associated with orthostasis / hypotension
- TEAEs associated with hypersensitivity

- TEAEs associated with slowing of ventricular repolarization
- TEAEs associated with hepatic effects
- TEAEs associated with sexual dysfunction

TEAEs associated with abuse potential will be presented by Adhoc System Organ Class and Preferred Term, where Adhoc System Organ Class is manually classified by Alkermes medical director as 3 categories: abuse behavior, euphoria related, and non-specific.

TEAEs associated with dependence will be presented for subjects with any exposure, ≥4 weeks exposure, and <4 weeks exposure, respectively.

PDEAEs associated with withdrawal will be presented for subjects with any exposure, ≥4 weeks exposure, and <4 weeks exposure, respectively. AESIs associated with withdrawal are PDEAEs that occur from >2 to 16 days post last dose as this is the period during which physiological opioid withdrawal presents by considering half-lives of both BUP and SAM.

Supportive AE listings will be provided for each special interest group. Narratives will be provided for clinically meaningful events within each AESI group.

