APPENDIX 3. AESI – WITHDRAWAL

Drug detoxification Reversal of opiate activity Drug rehabilitation Drug withdrawal convulsions Drug withdrawal headache Drug withdrawal maintenance therapy Drug withdrawal syndrome Drug withdrawal syndrome neonatal
Drug rehabilitation Drug withdrawal convulsions Drug withdrawal headache Drug withdrawal maintenance therapy Drug withdrawal syndrome
Drug withdrawal convulsions Drug withdrawal headache Drug withdrawal maintenance therapy Drug withdrawal syndrome
Drug withdrawal headache Drug withdrawal maintenance therapy Drug withdrawal syndrome
Drug withdrawal maintenance therapy Drug withdrawal syndrome
Drug withdrawal syndrome
Drug withdrawal syndrome neonatal
Rebound effect
Steroid withdrawal syndrome
Withdrawal arrhythmia
Withdrawal syndrome
Anhedonia
Depressed mood
Depression
Dysphoria
Feeling of despair
Morose
Negative thoughts
Persistent depressive disorder
Dyssomnia
Headache
Insomnia
Obsessive thoughts
Poor quality sleep
Syncope
Terminal insomnia
Agitation
Irritability
Anxiety
Chills
Hyperhidrosis
Nausea
Nervousness
Pain
Tremor
Vomiting
Abdominal pain
Arthralgia

Preferred Term	
Diarrhoea	
Mydriasis	
Piloerection	
Restlessness	
Rhinorrhoea	
Tachycardia	
Yawning	

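### The withdrawal AESI list mixes 12 depressive-mood and sleep terms with withdrawal terms, undivided, so a pooled withdrawal incidence could not be interpreted

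*Protocol*

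**What the plan says.** Protocol Section 8.1 calls the subject in for a COWS assessment if, in a follow-up call, any "AEs are reported that relate to opioid withdrawal (eg nausea, vomiting, restlessness, hyperhidrosis").

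SAP Section 3.7.3 sets the window: "AESIs associated with withdrawal are PDEAEs that occur from >2 to 16 days post last dose". Its reason is that "this is the period during which physiological opioid withdrawal presents", given the half-lives of the two components. AESIs in general "will be summarized by Preferred Term and by prior ALKS 5461 exposure and overall during treatment period", for the relevant safety population. For this group, "PDEAEs associated with withdrawal will be presented for subjects with any exposure", and then separately for at least 4 weeks and less than 4 weeks of exposure. Duration of exposure is the only subdivision.

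The terms are in SAP Appendix 3, as one list without classes. It runs from explicit entries such as Drug withdrawal syndrome, through low-mood entries such as "Persistent depressive disorder" and sleep entries such as "Terminal insomnia", to bodily symptoms such as Nausea and Piloerection.

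Abuse potential is handled differently. Its terms are "manually classified by Alkermes medical director as 3 categories: abuse behavior, euphoria related, and non-specific". SAP Appendix 1 shows the result, with Mood altered and Mood swings in the non-specific class.

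In follow-up (Protocol Table 3), COWS and C-SSRS are done at Visits 15 to 18 and CGI-S at Visits 16 to 18. MADRS is not scheduled after Visit 14.

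**The concern.** Every subject has MDD and, on entering follow-up, has just stopped a drug given to improve it. Low mood and poor sleep in the next two weeks have two ready explanations: opioid withdrawal, or depression worsening once the adjunct is removed. Section 3.7.3 has no causality filter, no rule for depressive worsening and no mood-versus-somatic split. The study has no reference therapy, so no control arm shows the background rate of such events.

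Withdrawal on stopping is an important safety question for a product containing buprenorphine, and much of the follow-up schedule is built to observe it. An undivided list can mislead in both directions. Depressive worsening could inflate the apparent withdrawal rate, and genuine withdrawal could be dismissed as relapse.

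**Working it through.** The plan states no rate or total for this AESI, so there is no figure to reproduce.

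**1. Count of Appendix 3 terms** (grouping is mine; no duplicates)

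| Group | Terms | n |
|---|---|---|
| Explicit withdrawal or its treatment | Drug withdrawal syndrome, Rebound effect, etc. | 12 |
| Low mood | Anhedonia, Depressed mood, Depression, Dysphoria, Feeling of despair, Morose, Negative thoughts, Persistent depressive disorder | 8 |
| Sleep | Dyssomnia, Insomnia, Poor quality sleep, Terminal insomnia | 4 |
| Anxiety or agitation type | Agitation, Anxiety, Irritability, Nervousness, Obsessive thoughts, Restlessness | 6 |
| Other somatic | Nausea, Vomiting, Chills, Tremor, etc. | 16 |
| Total | | 46 |

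Mood plus sleep: (8 + 4)/46 = 26% of all terms, or 12/(46 − 12) = 12/34 = 35% of the symptom-type terms. These are shares of dictionary terms, not of subjects or events.

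**2. Which instrument measures the 12 terms?** The COWS form (Protocol Appendix G) has 11 items. None scores depressed mood or sleep; one scores anxiety or irritability. The HAM-D guide (Appendix E) scores depressed mood and late insomnia, and the MADRS guide (Appendix H) scores sadness, sleep and pessimism. On the other side, MINI item J2b (Appendix D) counts poor sleep and feeling depressed among the symptoms of drug withdrawal. The protocol's own instruments therefore support both readings.

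**3. Can depressive worsening reach the table?** Protocol Section 13.1 records worsening of a pre-existing condition as an AE, and SAP Section 3.7.2 counts worsening as a PDEAE. It can, if it is reported as an AE, falls in the window and codes to a listed term.

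**4. Can subject counts be recovered from preferred-term rows?** If two rows show *a* and *b* subjects, the number with either event lies anywhere from max(*a*, *b*) to *a* + *b*. Section 3.7.2 counts a subject once per preferred term, so one subject can stand in several rows.

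**5. Illustration of size (assumed rates).** Let *p* be the proportion of subjects with any of the other 34 terms in the window and *q* the proportion with a mood or sleep term. Under independence the any-term incidence is *c* = 1 − (1 − *p*)(1 − *q*), and the share counted only through a mood or sleep term is (*c* − *p*)/*c*.

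| *p* | *q* | *c* | Share |
|---|---|---|---|
| 5% | 1% | 5.95% | 16% |
| 5% | 3% | 7.85% | 36% |
| 5% | 5% | 9.75% | 49% |
| 10% | 1% | 10.9% | 8% |
| 10% | 3% | 12.7% | 21% |
| 10% | 5% | 14.5% | 31% |

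If the events cluster in the same subjects, the share falls. It is zero when every subject with a mood or sleep term also has another listed term.

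**The case against.** Much of the case on the other side stands.

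- **No total is specified.** Section 3.7.3 describes summaries by preferred term, and the table shells are in a separate document (SAP Section 9). Depression and Insomnia would have their own rows. This stands: an any-term row is a possibility, not a stated output. Without one, however, the plan gives no subject-level withdrawal incidence at all. All AEs are listed by subject, so a count could be rebuilt, but with classes chosen after the data are seen.
- **The protocol and SAP do not conflict.** A reader might infer that the protocol defines withdrawal by bodily symptoms and the SAP departs from it. The protocol gives examples that prompt a COWS assessment, and restlessness is not purely somatic.
- **Mood and sleep terms can be genuine withdrawal symptoms.** MINI item J2b says so. This is why no term should be removed.
- **Other evidence exists.** COWS is analysed over the same window (SAP Section 3.7.8), CGI-S is summarised through follow-up (3.6.2.3), and each AESI group has listings and narratives. This helps, but nothing in the SAP links these results to the mood and sleep terms. The System Organ Class counts of PDEAEs are restricted neither to Appendix 3 terms nor to the window.
- **A broad list is the cautious choice for safety.** Separate classes keep that breadth.

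The SAP does not say why it divides the abuse-potential terms, so that division is a precedent for the method, not evidence of the same motive.

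**Conclusion.** The point holds as a matter of interpretability. Twelve of 46 withdrawal AESI terms can reflect either withdrawal or depressive worsening, and the plan neither separates them nor gives a subject count with and without them. A pooled incidence, if shown, could not be read as opioid withdrawal alone.

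A reader might go further and conclude that relapse will be reported as opioid withdrawal. The documents do not support that. An event is caught only if it is reported as an AE, starts or worsens after stopping, falls in the window and codes to a listed term, and even then its cause is ambiguous. This is confounding, not demonstrated misclassification.

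The size is unknown. The range of 8% to 49% above rests entirely on assumed rates and on independence. This is a cheap improvement to presentation, not a flaw that undermines the study.

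**What to change.** In SAP Section 3.7.3, before database lock, assign every Appendix 3 term to an ad hoc class, as for abuse potential:

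1. explicit withdrawal terms;
2. somatic, autonomic and other COWS-type symptoms;
3. mood and sleep terms (the 12 listed above).

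Report the number and percentage of subjects for each class, for classes 1 and 2 combined, and for all three. Keep the existing window, exposure groups and preferred-term rows, and keep every current term. Present class 3 beside the COWS analysis and the CGI-S change from Visit 14 to Visits 16 to 18.

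No new data are needed. The CGI-S comparison needs one derived variable, because Section 3.6.2.3 measures change from the pre-treatment baseline rather than from Visit 14. The cost is some SAP wording, a few table rows and a judgement on borderline terms such as Anxiety and Irritability, which must be fixed before lock. If all six anxiety or agitation terms went to class 3 instead of class 2, that class would have 12 + 6 = 18 of 46 terms (39%), so the assignment should be written down.
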